#### **3.2.4. Secondary Aim 1: Medication Effects on Alcohol Choice, Delay Discounting, and Alcohol Demand.**

One-way Analysis of Covariance (ANCOVAs) will be used to determine significant mean differences in crossover points on the multiple-choice paradigm, delay discounting, and alcohol demand between the medication groups (naltrexone, varenicline, and placebo). Mediation analyses will be used to determine whether the effects of medication on the multiple-choice paradigm were mediated by changes in discounting or demand for alcohol. Baseline covariates such as age, sex, and smoking status will be included in the model.

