#### 5.4.4. Alcohol Cue Reactivity Sessions (CR)

Randomized participants will complete a cue-exposure paradigm at two time points during the study, once on Day 1 prior to ingesting the first dose of study medication, and again on Day 14, approximately 90 minutes after study drug administration. Alcohol cue exposure will follow well-established experimental procedures. Sessions will begin with a 3-minute relaxation period. Participants will then hold and smell a glass of water for 3 minutes to control for the effects of simple exposure to any potable liquid. Next, participants will hold and smell a glass of their preferred alcoholic beverage for 3 minutes. Order is not counterbalanced because of carryover effects that are known to occur. Participants (who are smokers) will be allowed a smoke break immediately prior to the CR assessment. After every 3 minutes of exposure, participants will rate their urge to drink on the Alcohol Urge Questionnaire (AUQ) and their mood on the Profile of Mood States (POMS). AUQ score (alcohol minus water) is the primary outcome for the CR.

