#### **6.2.13. Monetary Choice Questionnaire (MCQ)**

The Monetary Choice Questionnaire is a 27-item self-administered questionnaire in which the participant chooses between a smaller, immediate monetary reward and a larger, delayed monetary reward. The MCQ will be completed at randomization and Day 14 visit, as part of the behavioral economics paradigm.

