### **3. STATISTICAL METHODS AND POWER CONSIDERATIONS**

#### **3.1. Statistical Power**

Power analyses were conducted using G\*Power 3.1.9.2. In order to conduct a one-way ANOVA with fixed effects, we estimated a medium-to-large effect size ( $f=0.40$  and an alpha error probability of 0.05). Specifically, with 3 groups a sample size of 90 completers, the proposed

study has an actual power of 0.91%. Therefore, we propose to randomize 108 individuals (36 in each group) to reach a final sample of 30 completers per group. This will allow us the statistical power to detect a medium-to-large effect size as projected.

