### **3.2. Data Analytic Plan**

Descriptive statistics will be computed for continuous outcome variables, and frequencies for categorical variables to summarize the study data. Box plots, histograms, and Q-Q plots will be used to check for skewness and normality for continuous variables. Transformations of continuous outcome variables will be performed as necessary to ensure that the normality assumptions in parametric tests are met. The models described below will test whether medication effects in reducing drinking behavior during the practice quit attempt are associated with concurrent blunting of cue reactivity. To improve model fit and hypothesis testing, we will consider covariates, such as age, sex, ethnicity, medication order, and AUD symptom count.

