#### **3.2.1. Primary Aim 1: To test that NTX and VAR will reduce drinking during the practice quit attempt as compared to placebo.**

A series of repeated measures ANCOVAs will be conducted using PROC GLM in SAS Statistical Software. Specifically, we will conduct repeated measures ANCOVAs on Percent Days Abstinent (PDA), and Drinks per Drinking Day (DPDD), our two co-primary outcomes, as predicted by Medication (NTX vs. PLAC and VAR vs. PLAC) a between-subjects factor and the covariate of baseline PDA and DPDD.

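### The delay-discounting ANCOVA in section 3.2.4 does not name the Day 1 Monetary Choice Questionnaire score as a covariate, which leaves available precision unsecured

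*Combined protocol and SAP*

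**What the plan says.** Section 3.2.4 (Secondary Aim 1) sets out the arm comparison: "One-way Analysis of Covariance (ANCOVAs) will be used to determine significant mean differences in crossover points on the multiple-choice paradigm, delay discounting, and alcohol demand". On covariates it says: "Baseline covariates such as age, sex, and smoking status will be included in the model". The general statement in section 3.2 reads "we will consider covariates, such as age, sex, ethnicity, medication order, and AUD symptom count". Neither list names the Day 1 MCQ score, and both are lists of examples.

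The score is collected. Section 6.2.13 states: "The MCQ will be completed at randomization and Day 14 visit, as part of the behavioral economics paradigm". The schedule in section 6.1 agrees. The same schedule puts the other two Secondary Aim 1 measures, the Multiple Choice Procedure and the Alcohol Purchase Task, on Day 14 only.

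Two other places bear on the point. Section 3.2.1 adjusts the co-primary drinking outcomes for "the covariate of baseline PDA and DPDD". The mediation analysis in section 3.2.4 asks whether medication effects on choice are "mediated by changes in discounting or demand for alcohol".

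**The concern.** An ANCOVA on a Day 14 score normally carries the same measure at baseline as its main covariate. The plan follows that practice for the co-primary outcomes. It does not state it for the one Secondary Aim 1 outcome that has a baseline on the same instrument.

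If the model is run with only the three covariates named, stable differences between people in discounting stay in the residual, although the trial has measured them. With about 30 completers per arm, that makes a real medication effect on discounting easier to miss. The arm comparison and the mediation analysis in the same section could also end up treating discounting differently, one as a Day 14 level and the other as a change. Finally, an open covariate list leaves the choice of adjustment to be made after the data are seen.

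**Working it through.** **Inputs from the documents (section 3.1).** Three groups, 90 completers (30 per arm), "an alpha error probability of 0.05", planning effect f = 0.40, stated power 0.91 (printed with a percent sign, evidently a slip of units). No power figure is given for delay discounting.

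**Assumed inputs.** The Day 1 to Day 14 MCQ correlation r, after the other covariates, is not in the documents; it is shown from 0.3 to 0.8. A pairwise difference of 0.5 SD and a smaller overall effect of f = 0.25 are also assumptions. Age, sex and smoking status are counted as 3 degrees of freedom with no explanatory power of their own.

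**Step 1: the plan's own figure.** One-way ANOVA, noncentral F with 2 and 87 degrees of freedom and noncentrality N·f² = 90 × 0.16 = 14.4. Power is 0.926, against the stated 0.91. The planning figure reproduces to within 2 points.

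**Step 2: variance.** Adjusting for a baseline with correlation r multiplies the variance of the arm difference by 1 − r². The equivalent number of completers without the covariate is 90/(1 − r²).

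| r | 1 − r² | Variance reduction | Equivalent completers |
|---|---|---|---|
| 0.3 | 0.91 | 9% | 99 |
| 0.5 | 0.75 | 25% | 120 |
| 0.7 | 0.51 | 49% | 176 |
| 0.8 | 0.36 | 64% | 250 |

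**Step 3: overall three-arm test.** Noncentral F with noncentrality N·f²/(1 − r²) and 83 denominator degrees of freedom (90 − 3 groups − 4 covariates). Without Day 1 MCQ there are 84 and r = 0.

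| Effect | Without Day 1 MCQ | r = 0.3 | r = 0.5 | r = 0.7 | r = 0.8 |
|---|---|---|---|---|---|
| f = 0.40 (planning value) | 0.926 | 0.948 | 0.978 | 0.998 | >0.999 |
| f = 0.25 (assumed) | 0.539 | 0.581 | 0.671 | 0.840 | 0.945 |

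At f = 0.40 the gain is 0.948 − 0.926 = 2.2 points at r = 0.3 and 0.978 − 0.926 = 5.2 points at r = 0.5.

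**Step 4: one active arm against placebo.** Two-sided 5% t test, 30 against 30, 58 degrees of freedom, noncentrality 0.5/√(1 − r²) × √(30/2).

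| | Without Day 1 MCQ | r = 0.3 | r = 0.5 | r = 0.7 | r = 0.8 |
|---|---|---|---|---|---|
| Power at 0.5 SD | 0.48 | 0.51 | 0.59 | 0.76 | 0.89 |

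Using the residual variance from all three arms instead of two changes these values by less than one percentage point.

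**Step 5: the price.** If r were zero, adding the covariate would cost one degree of freedom, which lowers power by less than 0.1 percentage point at either f = 0.40 or f = 0.25.

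**The case against.** The strongest reply is that the plan does not exclude the Day 1 score. Both covariate lists are introduced as examples, and a mediation analysis on changes in discounting implies that the Day 1 MCQ will be used there. This stands. A reader might infer that the trial ignores its own baseline; the documents support only that the score is not named for the arm comparison. An open list is still worth closing, because it fixes neither the covariate nor the scale.

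A second reply is that the gain may be small. This also stands in part. At the protocol's own planning effect, power for the overall test is already about 0.93, and the gain is 2 to 5 points at r = 0.3 to 0.5. Larger gains need a higher correlation or a smaller true effect, and the documents settle neither. They also do not show that age, sex and smoking status predict discounting poorly, or that Day 1 MCQ is the best predictor available. The recommendation needs neither claim.

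Third, a reader might infer that a chance Day 1 imbalance would bias the result. It would not. Under randomisation such imbalance is sampling error, already reflected in the standard error; the unadjusted estimate is unbiased and the type I error rate is not inflated.

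Fourth, it is tempting to treat the Day 1 MCQ as a pre-dose measure. The protocol says this only of the Day 1 cue-reactivity session ("once on Day 1 prior to ingesting the first dose of study medication", section 5.4.4). Section 6.2.13 places the MCQ at randomization, and section 5.4.3 has the first dose taken in the laboratory on the same day. The order of the two is not stated.

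**Conclusion.** The point holds as a gap in specification with a cost in precision. The plan collects a baseline for delay discounting and does not name it in the discounting ANCOVA, although it applies that principle to the co-primary outcomes. The validity of the comparison is not at risk.

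The size depends on an unknown correlation. It ranges from slight at r = 0.3 (9% less variance, 3 to 4 points of power for a 0.5 SD pairwise difference) to substantial at r = 0.8 (64% less variance, about 41 points). All power figures assume 30 completers per arm and no explanatory power from the other covariates.

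The point is limited to delay discounting. A reader might want to extend it to the crossover point and alcohol demand, but those are measured on Day 14 only, so the argument from a baseline on the same instrument does not reach them. This is a secondary aim; the primary analyses and the sample size are unaffected.

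**What to change.** In section 3.2.4, specify the discounting analysis as Day 14 MCQ score on arm, with Day 1 MCQ score as a prespecified covariate alongside age, sex and smoking status. State that both scores use the same scoring and the same transformation.

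Confirm in section 6.2.13 or the visit procedures that the Day 1 MCQ is completed before the first dose, so that it is a true baseline.

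The models for crossover point and alcohol demand need no change on this account. The cost is a sentence or two of text and one degree of freedom; no new data, visits or participant burden are needed.

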### **3.2.5. Secondary Aim 2: Alcohol Choice and Drinking Behavior During Practice Quit Attempt.**

Multiple regression analyses will be used to determine whether the number of drinks per drinking day and percentage of days abstinent during the practice quit attempt predict alcohol choice. Regression analyses will also include medication condition (naltrexone, varenicline, placebo) as a moderator of the relationship between alcohol drinking behaviors during the practice quit attempt and alcohol choice. Baseline covariates such as age, sex, and smoking status will also be included in the model.

### **3.2.6. Exploratory Aim**

We will conduct direct comparisons between the two active medications (VAR vs. NTX) as part of the exploratory analyses for the study.

## **4. ETHICS**

### **4.1. IRB Review**

The study will be conducted under a protocol reviewed by the UCLA IRB; the study is to be conducted by scientifically and medically qualified persons; the benefits of the study are in proportion to the risks; the rights and welfare of the subjects will be respected; the physicians conducting the study will ensure that the hazards do not outweigh the potential benefits; the results to be reported will be accurate; subjects will give their informed consent and will be competent to do so and not under duress; and all study staff will comply with the ethical principles in 21 Code of Federal Regulations (CFR) Part 50 and the Belmont Principles.

#### **4.1.1. Protocol Modifications**

All necessary protocol changes will be submitted in writing as protocol amendments to the IRB by the PI for approval prior to implementation.

#### **4.1.2. Protocol Deviation Reporting Procedures**

All subject-specific deviations from the protocol are to be documented. The PI or designee will be responsible for identifying and reporting all deviations, which are occurrences involving a procedure that did not follow the study protocol. Any protocol deviation that adversely affects the safety or rights of a subject or scientific integrity of the study is considered a major deviation and will be reported immediately to the UCLA IRB.

### **4.2. Ethical Conduct of the Study**

This study will be conducted in accordance with all applicable Federal human research protections requirements and the Belmont Principles of respect for persons, beneficence, and justice. The procedures set out in this study are designed to ensure that all study personnel abide by the principles of the ICH GCP Guideline and the Code of Federal Regulations (CFR). The PI confirms this by signing FDA Form 1572.

#### **4.2.1. Confidentiality of Data and Subject Records**

To maintain subject confidentiality, all laboratory specimens, eCRFs, reports and other records will be identified by a subject number only. Research and clinical records will be stored in a locked cabinet. Only research staff, and other required regulatory representatives will have access to the records. Subject information will not be released without written permission. The PI has received a Certificate of Confidentiality for this study.

#### 4.2.2. Compensation for Participation

Subjects will be compensated for travel expenses and for time contributed to this research study in the form of cash. Compensation will be provided at each subject visit and is detailed in the informed consent form.

#### 4.2.3. Written Informed Consent

The informed consent process and document will be reviewed and approved by the IRB and prior to initiation of the study. The consent document contains a full explanation of the possible risks, advantages, and alternate treatment options, and availability of treatment in the case of injury, in accordance with 21 CFR Part 50. The consent document indicates that by signature, the subject, permits access to relevant medical records as described above. A written informed consent document, in compliance with 21 CFR Part 50, 32 CFR Part 219, and the Belmont Principles, and HIPAA Authorization will be signed by the subject before any study-related procedures are initiated for each subject. All potential subjects for the study will be given a current copy of the Informed Consent Form to read. All aspects of the study and informed consent will be explained in lay language to the subject by either the investigator, or a medically trained designee. Any subject who is unable to demonstrate understanding of the information contained in the informed consent will be excluded from study participation. All study subjects will be given a copy of the signed informed consent.

#### 4.2.4. Delegation of Responsibilities and Adequate Resources

The PI should have adequate time to conduct the study properly and should have an adequate number of qualified staff to assist with the conduct of the study. The term “investigator” used throughout this protocol refers to the PI and/or qualified Sub-investigators. The PI may delegate responsibilities to other study site personnel. The PI shall delegate tasks only to individuals qualified by education, training, and experience to perform the delegated tasks. The PI shall have direct oversight of all delegated activities and shall document delegation of responsibilities. The PI is responsible for ensuring all delegated staff has been properly trained on the protocol and their assigned study responsibilities. A delegation log identifying all delegated duties and the individual to whom they have been delegated will be maintained at the study site.

#### 4.2.5. Financial Disclosure

Clinical investigators are required to provide financial disclosure information for the submission of certification or disclosure statements required under 21 CFR § 54. As defined in 21 CFR §54.2, a clinical investigator is a listed or identified investigator or sub-investigator who is directly involved in the treatment or evaluation of research subjects. The term also includes the spouse and each dependent child of the investigator. In addition, investigators must promptly update financial disclosure information if any relevant changes occur during the course of the investigation and for 1 year following completion of the study.

## **5. DATA HANDLING AND RECORD KEEPING**

Source documents include but are not limited to original documents, data and records such as hospital/medical records (including electronic health records), clinic charts, laboratory results, data recorded in automated instruments, and pharmacy records, etc. This study will use an electronic data capture (EDC) eCRF system (Qualtrics) and paper source documents. Data will be transcribed from source documentation directly into a statistical program such as SPSS. Only questionnaire data will be entered directly into eCRF (i.e., without prior written or electronic record of data). Paper copies of the eCRFs will be available in the event that the EDC is not accessible at the time the questionnaire is being completed. The transcribed data will be consistent with the source documents or the discrepancies will be explained. All entries, corrections, and alterations will be made by the investigator or other authorized study personnel. The EDC system maintains a full audit trail of data entry, data corrections, and data queries.

### **5.1. Subject Identification and Confidentiality**

Subjects will be identified on eCRFs and paper source documents by a unique subject number. No personal identifier will be used in any publication or communication used to support this research study. The subject number will be used if it becomes necessary to identify data specific to a single subject. Regulatory bodies, such as the FDA and IRB, are eligible to review medical and research records related to this study as a part of their responsibility to protect human subjects in clinical research. Personal identifiers will be removed from photocopied or electronic medical and research records.

### **5.2. Retention of Records**

The investigator is responsible for creating and/or maintaining all study documentation required by Title 21 Code of Federal Regulations (21CFR) Parts 50, 54, 56, and 312, ICH E6 section 8, as well as any other documentation defined in the protocol. Federal and local regulations require that the investigator retain a copy of all regulatory documents and records that support the data for this study for whichever of the following is the longest period of time:

- A period of 2 years following the final date of approval by the FDA or other regulatory agency of the study drug for the purposes that were the subject of the investigation; or
- A period of 5 years following the date on which the results of the investigation were submitted to the FDA or other regulatory agency in support of, or as part of, an application for a research or marketing permit for the study drug for the purposes that were the subject of the investigation.

If the investigator retires, relocates, or for other reasons withdraws from the responsibility of keeping the study records, custody must be transferred to a person who will accept the responsibility.

